5.2.2.2 Hypotension

Hypotension, presents as paleness and perspiration, with lowered blood pressure and bradycardia. This AE appears as a result of a vasovagal response secondary to hypothalamic stimulation, and is very rarely attributable to volemia if the separator used is of the continuous flow type (seen historically in approximately 2.6% of all processes).

The predisposing factors may be patient-related (low body weight, a history of vasovagal reactions, or a low hematocrit) or related to the procedure (equipment fatigue or extracorporeal volume >20% of patient volemia).

The initial symptoms and signs include:

- perspiration
- bradycardia
- hypotension

The progressive manifestations comprise:

- nausea
- vomiting
- syncope
- involuntary defecation
- seizures

Treatment of hypotension consists of interrupting the process, opening the serum access, placing the patient horizontal or in the Trendelenburg position, recording blood pressure and pulse, and waiting for recovery while investigating the cause (disconnect in case of equipment leakage; if other cause is involved, assess continuation). Recommendations for preventing hypotension related events in low-volume plasma exchange procedures have been captured in a study guideline. Hypotension episodes can be avoided by infusing saline solution and adjusting the removed plasma volume in low-weight patients (see Appendix 10).

5.2.2.3 Allergic reaction

Allergic reactions are generally associated with the blood components and albumin, though they may also be due to ethylene oxide or other medication.

The signs and symptoms include:

- urticaria
- dyspnea
- wheezing
- hypotension
- tachycardia
- facial reddening
- palpebral edema

In case the patient suffers from an allergic reaction the site should follow their standard procedures to manage the situation. As a recommendation, mild allergic reactions could be controlled with antihistamines (diphenhydramine 25-50 mg i.v.). In case the reaction continues, or in the event of anaphylactic manifestations, it could be administered 0.3-0.5 mL of epinephrine 1:1000 s.c. This dose may be repeated after 10-15 minutes if no response is elicited. It is also possible to add methylprednisolone 100 mg i.v.

5.2.2.4 Coagulation disorders

When the extracted plasma is replaced with albumin, coagulation disorders may develop due to dilution of the coagulation factors, mainly lowered blood fibrinogen, since its half-life is 72 hours. During daily plasma exchange sessions the fibrinogen concentration may drop to below 1 g/L, requiring the infusion of plasma or fibrinogen. When replacement is performed every 72 hours, such measures are not necessary.

Minor bleeding associated with severe thrombopenia has been observed (seen historically in approximately 2.2%).

5.2.2.5 AEs Related to vascular access

The central catheter has the advantage of increased convenience for the subject during the process, since it allows greater flows and thus shorter session times, obviating the need in each session to perform two peripheral venipunctures.

As to the adverse effects if the catheter is placed in the subclavian vein, the risk of infection is minimal. Thus, while the incidence of infections with all the catheters is <5 per 1000 days (<3% of all catheters), this incidence decreases considerably if only those placed in the subclavian vein are considered^{23,24}. Pneumothorax, hemothorax, bleeding at the time of placement and thrombosis in the case of indwelling catheters left in place for extended periods of time may be seen. The recommendations for the treatment and prevention of fever management and thromboembolic events have been captured in two study guidelines (see Appendix 11 and Appendix 12, respectively); nonetheless the sites should follow their local procedures.

As to adverse events related to peripheral access, the most commonly expected are: pain, phlebitis, infiltration and extravasation.

5.2.2.6 Other AEs and their treatment

Other potential AEs include headache, nausea and anxiety.

- Headache: administer paracetamol (acetaminophen) p.o. 1 g
- Nausea: administer Primperan p.o. (Reglan) 5 mL
- Anxiety: administer diazepam p.o. 5 mg (for body weight <55 kg) or 10 mg (weight > 55 kg), or alprazolam at doses of 0.5 mg and 1 mg, respectively
- IG levels decrease: A decrease in the IGs levels could occur during the FPE period. IG levels will recover their normal range at the end of the FPE period. Further investigations will be needed if the levels are not reestablished which may suggest an underlying pathology
- Anemia: Although not frequently, it is expected to observe anemia in patients with haematocrit in the low normal range after the first FPEs. In these cases, oral or intravenous iron therapy is recommended depending on the severity of the anemia and the investigator assessment

The recommendations to treat those AE are described above; nevertheless, the sites should follow their local procedures.

5.2.2.7 Incidence of adverse reactions and mortality

In a 1996 review of the adverse effects of plasma exchange in patients with Guillain-Barré syndrome, involving albumin replacements, a decrease in immediate adverse effects from

12% in 1986 to 7% in 1992 was recorded. Allergic reactions and hypotension were the most frequent problems. The estimated mortality was 1-2 deaths per 10,000 sessions, or two deaths per 2000 patients.

As stated earlier, the expected rate of AEs during the plasmaphereses of the low-volume plasma exchanges (Maintenance period) is much lower than that expected during the full plasma exchanges (Intensive period). For the expected adverse reactions relative to Albutein[®] and Flebogamma[®] DIF see **Section 9.1.3** and the corresponding **Full Prescribing Information (Appendix 1 and 2)**.

5.3 Concomitant Treatment

Subjects may continue to receive his/her usual medication. In particular, the same acetylcholine esterase inhibitor (AChEI) and/or memantine treatment is to be continued, without modification during the study. If the subject develops adverse reactions related with the AChEI and/or memantine treatment, advising its withdrawal, the medication should be replaced by another drug of the same group at the end of all the plasma exchanges.

Regarding IVIG administrations, the subject can be premedicated with paracetamol and antihistamines or corticosteroids at the discretion of the investigator. There are some sites that include corticosteroids administration during immunoglobulin infusion.

Treatment with angiotensin-converting-enzyme inhibitors (ACEIs) is not allowed during the study. Principal Investigator may consider changing the medication to other antihypertensive drug at the screening visit and maintaining throughout the study.

Any medication administered during the study (including any blood products) will be recorded on the case report form (CRF).

5.4 Special Guidelines for Study Drug Handling

Albutein[®] and Flebogamma[®] DIF that are supplied for use in the trial are to be destined exclusively to the study. Any unused material must be returned to the sponsor or at the discretion of the sponsor, may be destroyed at the center according to their SOPs.

The investigator (or pharmacist) or designated team member is to keep all records of drug utilization. The sponsor will provide specific forms to be completed by the investigator, pharmacist or designated team member, at the time of dispensation. These forms can be replaced by proprietary forms of the study center, provided they meet the requirements of the sponsor.

Once the forms have been completed, they must be signed and dated by the monitor and by the investigator to confirm their accuracy.

5.4.1 Storage of Albutein[®] and Flebogamma[®] DIF

Albutein[®] is to be stored at a temperature below 30°C. The shelf life is three years when maintained at this temperature.

The product should not be frozen. Once the container is open, the contents must be administered immediately. Unused contents must be discarded according to the Center's SOP. No remaining product in an opened container can be stored in the refrigerator and used at a later time. This product must not be used beyond the expiry date stated on the labeling.

The solution is normally clear to slightly opalescent. Do not use the IP if the solution is cloudy or has precipitated.

The product must be warmed to body temperature before use.

Access to the product must be strictly limited.

Flebogamma[®] DIF is a liquid product and then reconstitution is not necessary. Flebogamma[®] DIF should be stored below 25°C, should not be frozen and has a shelf-life of two years when stored at this temperature. It must not be frozen and the unused contents of the vial should be kept separately until drug accountability has been completed. Vials must be inspected for particles and discoloration before administration. Solutions with evidence of turbidity should not be used because of the risk of bacterial contamination. Flebogamma[®] DIF must not be mixed with other pharmaceutical products or intravenous solutions, and a dedicated sterile infusion line should be used to ensure proper administration. Flebogamma[®] DIF must be brought to room temperature before infusion and administered intravenously through a separate infusion line. Mixing and administration of any other drug (including normal saline) with Flebogamma[®] DIF is strictly prohibited.

5.5 Measures to Assess Compliance

Such measures are not applicable, since the procedure is carried out under the supervision of the principal investigator, and in the hospital setting.

5.6 Rescue Medication

No rescue medication is being provided under the clinical trial. The principal investigator is responsible for follow-up of the medical needs of the subject. During the treatment phase, the physician supervising the plasma exchanges will propose the adequate measures according to the condition of the subject.

6. TRIAL CONDUCT AND RESPONSE ASSESSMENT

6.1 Study Variables

6.1.1 Primary Efficacy Variable

Change from baseline in the cognitive scores as measured by ADAS-Cog (6 measurements: weeks -3, -2 or -1 and 7-8; months 6, 9, 12 and 14) within the 3 treatment arms.

Change from baseline in the ADCS-ADL inventory (6 measurements: weeks -3, -2 or -1 and 7-8; months 6, 9, 12 and 14) within the 3 treatment arms.

Since it has been suggested that systemic infections can have a detrimental effect on cognitive scores, monitoring of subjects for number and type of bacterial infections requiring antibiotics will be performed.

6.1.2 Secondary Efficacy Variables

- a) Change from baseline in the cognitive, functional and neuropsychiatric scores and overall development as measured by MMSE, NPS battery, NPI, CDR-Sb, ADCS-CGIC, CSDD and C-SSRS. (6 measurements: week -3, -2 or -1 and 7-8; months 6, 9, 12 and 14) and QoL-AD, RUD-Lite[®] (5 measurements: weeks -3, -2 or -1; months 6, 9, 12 and 14). Moreover the optional questionnaires like OAS and ABS could be used at any visit in case any sign of aggression or restlessness.
- b) Variation in levels of A β ₁₋₄₀ and A β ₁₋₄₂ in CSF in the period between baseline lumbar puncture (before the start of the Intensive treatment period) and lumbar puncture immediately after the end of the last low-volume plasmapheresis (whenever this may be)
- c) Variation in the levels of A β ₁₋₄₀ and A β ₁₋₄₂ in CSF between the finalization and beginning of each of the 2 treatment periods.
- d) Levels of A β ₁₋₄₀, A β ₁₋₄₂, T-tau and P-tau in CSF throughout the study.

- e) Plasma levels of A β ₁₋₄₀ and A β ₁₋₄₂ before and after each plasma exchange for both treatment periods.
- f) Structural changes in volume of the hippocampus, posterior cingulate area, and other associated areas by MRI. Five measurements will be made (weeks -3, -2 or -1 and 7-8; months 6, 9 and 14).
- g) Variation in FDG-PET patterns (4 measurements: weeks -3, -2 or -1 and 7-8; months 9 and 14).

6.1.3 Safety Variables

The primary criterion of safety will be the percentage of plasma exchanges (full and low-volume exchanges, including the infusion of albumin and IVIG) associated with at least one adverse event that may be related to the study procedure (adverse reactions). In addition, consideration globally will be made of the percentage plasma exchanges (full and low-volume exchanges, including the infusion of albumin and IVIG) involving some adverse event, whether or not related to the procedure.

Vital signs (blood pressure, heart rate, respiration rate, and body temperature) will be recorded before, during and after each plasma exchange session, where required. Evaluation will also be made (where required) of the different laboratory test parameters (blood cell counts, platelet count, prothrombin time (Quick), aPPT, fibrinogen, total proteins, and calcium).

During the treatment periods (before each plasma exchange) and on the days when there is no replacement, anxiety and restlessness tests will be made based on the Overt Aggression Scale (OAS) and the Agitated Behavior Scale (ABS), whenever considered opportune.

According to the criterion of the investigator, all the clinically important changes in vital function, laboratory test parameters and neuroimaging findings will be evaluated.

6.2 Conduction of the Trial. Study Procedures.

See **Appendix 8** for the **Study Summary Table** and for the **Study Flow Chart**.

6.2.1 Screening Visits (Weeks -3, -2 and -1)

After obtaining informed consent, there will be screening period of up to 3 weeks which could consist of multiple visits. During the screening visit, all demographic data will be collected. Documentation will also include vital signs (axillary temperature, heart and respiration rate, and blood pressure) and physical examinations with ECG and a sample of blood for genetic markers determination.

Also at the screening visit, the subject's medical history, including AD, will be recorded together with the medication used in the preceding month. The CRF will also register a brief history of AD and the prior treatments received. However, on subsequent visits, recording will be limited to the abnormal conditions observed during the previous visit, along with the concomitant medication and any adverse event that may have been detected.

Sufficient blood will be collected for all the laboratory tests, and a plasma sample will be stored at -70°C for any possible future analysis.

The following parameters will also be evaluated: biomarkers of AD (A β -40, A β -42, β -secretase, γ -secretase, cholesterol, LDL, HDL, VLDL, C-reactive protein, rheumatoid factor, IL-1b, IL-6, ferritin, TNF- α), coagulation factors (prothrombin time (Quick), aPPT, calcium

and fibrinogen), proteinogram (total proteins, albumin, α 1-globulina, α 2-globulina, β -globulina, γ -globulina and IgG), other liver or kidney biochemical markers (AST, ALT, bilirubin, LDH and creatinine), troponin and serology (anti-HIV and HCV antibodies, and HBsAg antigen). In addition, a blood cell count will be performed, including: hematocrit, hemoglobin and erythrocytes, platelets and leukocytes (if an abnormal leukocyte count is recorded, it will be obligate to specify neutrophils, basophils, eosinophils, lymphocytes and monocytes).

All the inclusion criteria are to be confirmed again after obtaining the laboratory test results. If the inclusion criteria are not met, or if some exclusion criterion proves applicable, the patient may not be entered into the study.

During the study period between week -3 and the first plasma exchange (week 0), MRI and FDG-PET will be performed.

At the same time, during this study period (from week -3 to week 0), the following tests will be administered to measure cognition, functionality, behavior, global evolution, impression and depression : MMSE, ADAS-Cog, NPS battery, ADCS-ADL, NPI, CDR-Sb, ADCS-CGIC, CSDD, CSSRS, QoL-AD and RUD-Lite[®] which are to be administered as indicated in the corresponding section. Likewise, anxiety and restlessness tests will be made based on the Overt Aggression Scale (OAS) and the Agitated Behavior Scale (ABS), whenever considered opportune.

If the subject is to receive full plasma exchanges through a central venous access, a double-lumen catheter will be placed in the subclavian or jugular vein before the full plasma exchange period. It is advisable to place the catheter a few days before the first plasma exchange session. For the low-volume exchanges peripheral access will be used.

Furthermore, it is obligatory to perform lumbar puncture before the first plasma exchange, to collect CSF samples and assess the levels of A β -40, A β -42, P-tau, T-tau, β -secretase, γ -secretase, cholesterol, LDL, HDL, VLDL, C-reactive protein, IL-1b, IL-6, ferritin, TNF- α) and to perform standard CSF tests (cell counts, glucose, proteins and albumin). Time collection for the CSF must be between 8am and 12am. If these procedures are not carried out in the days preceding plasma exchange, they will have to be done on the day of first plasma exchange with the subject remaining at rest until indication by the investigator that plasma exchange can be carried out. These evaluations are considered to be the baseline data.

6.2.2 Weeks 1 to 6 - Intensive plasma exchange period

Full Plasma Exchange (Window range +/- 1 day)

Plasma samples will be collected from the subject before and 15-30 minutes after each procedure, to allow the pertinent tests. Additional plasma samples will be collected each time for storage at -70°C and possible future assays.

The following tests will be made before each procedure: biomarkers of AD (A β -40, A β -42, β -secretase, γ -secretase, cholesterol, LDL, HDL, VLDL, C-reactive protein, rheumatoid factor, IL-1b, IL-6, ferritin and TNF- α), coagulation factors (prothrombin time (Quick), aPPT, calcium and fibrinogen) and proteinogram (total proteins, albumin, α 1-globulina, α 2-globulina, β -globulina, γ -globulina and IgG). In addition, a cell count will be made including hematocrit, hemoglobin and erythrocytes, platelets and leukocytes (if an abnormal leukocyte count is recorded, it will be obligate to specify neutrophils, basophils, eosinophils, lymphocytes and monocytes). The samples obtained after plasma exchange will be used to evaluate the biomarkers of AD, cell count, platelets, coagulation factors (prothrombin time

(Quick), aPPT, calcium), proteinogram, fibrinogen and troponin, as well as other biochemistry parameters (AST, ALT, LDH and creatinine).

A maximum of six full plasma exchange sessions will be made during this period: one per week.

The subject will remain in the center throughout the procedure and then for as long as needed to ensure a safe return home, under conditions similar to before plasma exchange.

Before plasma exchange, a physical examination will be made, with the recording of any anomalies. Concomitant medication is also to be registered, together with any adverse event detected since the last visit or since the last plasma exchange session. The anxiety and restlessness tests, if necessary, will be performed before each plasma exchange process, and between 15-30 minutes after replacement. These tests will be carried out by the same patient supervisor.

Vital signs (axillary temperature, heart and respiration rate, and blood pressure) will be determined 15-30 minutes before replacement during and again 15-30 minutes after the procedure, and as often as considered opportune by the investigator.

Any adverse event during or after the procedure, will be recorded.

Control group

The control group will undergo simulated (sham) full plasma exchanges and will follow the same schedule of assessments including the lumbar puncture.

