5.1.2 Dosage and Treatment Regimen

The six full replacement sessions of the intensive treatment period will be completed in six weeks (one session per week)

The volume of each full plasma exchange will be approximately that of one plasma volume of the patient as calculated from body weight, height and hematocrit (approximately 35-45 mL/kg, corresponding to a volume of 2500-3000 mL).

The 12 low-volume plasma exchange sessions (9 with albumin 20% and 3 with IVIG) of the maintenance treatment period will be completed in 12 months (one session per month).

The volume of each plasmapheresis during the low-volume plasma exchange period will be between 690 and 880 mL of plasma (depending on the patient body weight, following the nomogram for plasma donation used in the USA. (See **Appendix 3**).

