5.1.3 Method of Application

Full plasma exchanges (Intensive treatment period)

Full plasma exchanges (FPE) can be carried out via peripheral access or centrally, according to the individual characteristics of the subject. In the latter case, and before the first replacement session, a double-lumen catheter must be placed in the subclavian or jugular vein. Implantation and maintenance will be carried out according to the standard procedures used in each center but it will be mandatory to perform a chest X-ray to confirm the correct placement of the catheter. Removed plasma volume will be replaced with the same volume of Albutein[®] 5% during the procedure.

The removed and replaced plasma volume will depend on patient's characteristics (sex, height, weight and hematocrit). It will be approximately 35-45 mL/kg, corresponding to a volume of 2500-3000 mL. This volume is calculated automatically by the device or manually by the operator depending on the device used.

For blinding the control group, adhesive gauze dressing will be placed on the subclavicular or jugular region, stitching a catheter of characteristics similar to the catheters used in the treatment group (see Appendix 9).

The central catheter has the advantage of increased convenience for the subject during the process, since it allows greater flows and thus shorter session times and obviates the need in each session to perform two peripheral venipunctures. The central line access also facilitates subject mobility during the procedure.

Each session is carried out at a rate of 60-100 mL/min., provided replacement is possible through a double-lumen catheter placed in the subclavian vein, with a continuous-flow cell separator. Each of these sessions will last approximately two to three hours. The control group will be subjected to simulated (sham) plasma exchanges during the same time as the subjects in the treatment group.

Each subject must remain in the facility throughout the procedure and then for as long as necessary to ensure a safe return home.

These details refer to the plasma exchange procedure performed through centrifugation (the most commonly used) although the procedure through filtration is also permitted.

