| Window Range (days) | | | | +/- 1 | +/- 1 | +/- 1 | +/- 1 | +/- 1 | +/- 1 | +/- 2 | +/- 5 | +/- 5 | +/- 5 | +/- 5 | +/- 5 | +/- 5 | +/- 5 | +/- 5 | +/- 5 | +/- 5 | +/- 5 | +/- 5 | +/- 2 | |
| Months | -1 | | | 1 | | | | 2 | | | 3 | 4 | 5 | 6 | 7 | 8 | 9 | 10 | 11 | 12 | 13 | 14 | 14 | |
| Laboratory Tests | | | | | | | | | | | | | | | | | | | | | | | | |
| Blood cell counts | X | | | B+A | B+A | B+A | B+A | B+A | B+A | | B | B | B | B | B | B | B | B | B | B | B | B | B | X |
| Platelet counts | X | | | B+A | B+A | B+A | B+A | B+A | B+A | | B | B | B | B | B | B | B | B | B | B | B | B | B | X |
| Prothrombin time (Quick) | X | | | B+A | B+A | B+A | B+A | B+A | B+A | | B(X) + A(O) | B(X) + A(O) | B(X) + A(O) | B(X) + A(O) | B(X) + A(O) | B(X) + A(O) | B(X) + A(O) | B(X) + A(O) | B(X) + A(O) | B(X) + A(O) | B(X) + A(O) | B(X) + A(O) | X | |
| aPTT | X | | | B+A | B+A | B+A | B+A | B+A | B+A | | B(X) + A(O) | B(X) + A(O) | B(X) + A(O) | B(X) + A(O) | B(X) + A(O) | B(X) + A(O) | B(X) + A(O) | B(X) + A(O) | B(X) + A(O) | B(X) + A(O) | B(X) + A(O) | B(X) + A(O) | X | |
| Fibrinogen | X | | | B+A | B+A | B+A | B+A | B+A | B+A | | B | B | B | B | B | B | B | B | B | B | B | B | B | X |
| Proteinogram | X | | | B+A | B+A | B+A | B+A | B+A | B+A | X | B | B | B | B | B | B | B | B | B | B | B | B | B | X |
| Plasma IgG | X | | | B+A | B+A | B+A | B+A | B+A | B+A | X | B(X) + A(O) | B(X) + A(O) | B(X) + A(O) | B(X) + A(O) | B(X) + A(O) | B(X) + A(O) | B(X) + A(O) | B(X) + A(O) | B(X) + A(O) | B(X) + A(O) | B(X) + A(O) | B(X) + A(O) | X | |
| Calcium | X | | | B+A | B+A | B+A | B+A | B+A | B+A | | B(X) + A(O) | B(X) + A(O) | B(X) + A(O) | B(X) + A(O) | B(X) + A(O) | B(X) + A(O) | B(X) + A(O) | B(X) + A(O) | B(X) + A(O) | B(X) + A(O) | B(X) + A(O) | B(X) + A(O) | X | |
| AST | X | | | A | A | A | A | A | A | | | | | | | | | | | | | | | X |
| ALT | X | | | A | A | A | A | A | A | | | | | | | | | | | | | | | X |
| Bilirubin | X | | | | | | | | | | | | | | | | | | | | | | | X |
| LDH | X | | | A | A | A | A | A | A | | | | | | | | | | | | | | | X |
| Creatinine | X | | | A | A | A | A | A | A | | | | | | | | | | | | | | | X |
| Troponin * | X | | | A | A | A | A | A | A | | | | | | | | | | | | | | | X |
| Anti-HIV | X | | | | | | | | | | | | | | | | | | | | | | | X |
| HCV antibodies | X | | | | | | | | | | | | | | | | | | | | | | | X |
| HBsV Ag | X | | | | | | | | | | | | | | | | | | | | | | | X |

FPE: Full Plasma Exchange

LVPE: Low-Volume Plasma Exchange

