7.2.4 Clinical Laboratory Tests

Summary statistics for biochemistry, proteinogram, hematology, and clotting laboratory tests will be presented at each visit. Actual values and changes from baseline to each visit will be summarized using descriptive statistics. All changes will be changes from the baseline value, there will be no comparisons in the values between the pre- and post FPE values. Maximal shifts from baseline during the FPE and during the LVPE will be summarized using the CTC AE grading system Version 4.03 and patient counts. Shifts for laboratory values which have no CTC AE grade will be based on the normal ranges (below, within, and above the normal range, if applicable).

	Title: Statistical Analysis Plan
	Project #: IG1002 AMBAR
	Version: Final 1.0 Effective Date: 31July2018
	Protocol Version: Version 5.0 Effective Date: Feb2018

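### At the six full exchanges, liver enzymes, LDH and troponin are sampled only after the plasma has been exchanged, which biases active-arm values downward against sham and against baseline

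*Protocol*

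**What the plan says.** **Sampling.** Protocol 6.2.2 draws blood twice per session: "Plasma samples will be collected from the subject before and 15-30 minutes after each procedure". The pre-exchange list begins "The following tests will be made before each procedure: biomarkers of AD" and continues with coagulation, proteinogram and cell count. AST, ALT, LDH, creatinine and troponin are not on it. They appear only for the post-exchange sample: "fibrinogen and troponin, as well as other biochemistry parameters (AST, ALT, LDH and creatinine". The laboratory table in Appendix 8 agrees. These five rows carry the letter A (after) alone at FPE1-FPE6, while cell counts, coagulation, fibrinogen and proteinogram carry B+A.

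**Exchange.** Protocol 5.1.2: "The volume of each full plasma exchange will be approximately that of one plasma volume of the patient". Protocol 5.1.3: "Removed plasma volume will be replaced with the same volume of" Albutein 5%.

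**Sham.** Protocol 6.2.2 gives control patients the same assessment schedule. Protocol 3.3 and Appendix 9 state that no fluid is exchanged, and Appendix 9 makes their blood draws before and after the session real.

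**Analysis.** SAP 7.2.4 summarises change from baseline, rules out comparing pre- with post-FPE values, and adds: "Maximal shifts from baseline during the FPE and during the LVPE will be summarized using the CTC AE grading system". SAP section 7 defines baseline as the last assessment before the first exchange or sham session. For by-visit safety summaries it takes the last non-missing assessment at a visit.

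**Later visits.** Neither Protocol 6.2.3 nor Appendix 8 repeats the five analytes at the intermediate visit. Protocol 6.2.4 says they will be done in the maintenance period, but Appendix 8 leaves their cells blank for LVPE1-LVPE12.

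**The concern.** A blood value taken minutes after a one-volume exchange reflects the patient's level and also how much of the analyte has just been removed. In the active arms both parts are present; in sham only the first is. The two are then tabulated side by side and graded against a baseline that had no exchange before it.

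At stake is the laboratory evidence on liver, tissue and heart during the most intensive part of treatment. On the Appendix 8 schedule, an active-arm patient has no unwashed value of these markers between screening and the final visit. If 6.2.4 governs instead, the gap runs to the maintenance period. A mild or moderate rise could sit inside the normal range in the shift tables for active patients while the same rise would show in a sham patient.

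**Working it through.** The plan states no washout fraction, so there is no figure to reproduce. The size below is a model result.

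**Inputs from the documents**
- Volume exchanged: about 1.0 plasma volume (Protocol 5.1.2). The range 0.8-1.2 is my assumption for how loosely 'approximately' may be met.
- Sample time: 15-30 minutes after the session (6.2.2).
- Session length: "Each of these sessions will last approximately two to three hours" (5.1.3).
- Sham washout: 0%, since nothing is exchanged.
- Illustrative level: ALT (GPT) 2.5 x ULN, the limit in exclusion criterion 11 (4.1.2).

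**Step 1: one well-mixed compartment, no refill.** Fraction remaining = exp(-V/PV).

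| V/PV | Remaining | Removed | 2.5 x ULN reads | Reads normal up to | True value needed to read 2.5 x ULN |
|---|---|---|---|---|---|
| 0.8 | 0.449 | 55.1% | 1.12 x | 2.23 x | 5.56 x |
| 1.0 | 0.368 | 63.2% | 0.92 x | 2.72 x | 6.80 x |
| 1.2 | 0.301 | 69.9% | 0.75 x | 3.32 x | 8.30 x |

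At V/PV = 1.0, a true 3 x ULN reads 3 x 0.368 = 1.10, 5 x reads 1.84 and 10 x reads 3.68.

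**Step 2: allow refill from outside plasma.** If refill is instant and complete, and a share f of the analyte is in plasma, fraction remaining = exp(-f x V/PV). With V/PV = 1.0:

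| f (assumed) | Removed | 2.5 x ULN reads |
|---|---|---|
| 0.8 | 55% | 1.12 x |
| 0.6 | 45% | 1.37 x |
| 0.4 | 33% | 1.68 x |
| 0.1 | 10% | 2.26 x |

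At 50% removal, 2.5 x ULN reads 1.25 x and 3 x reads 1.5 x. Washout acts downward in every row. The last row is an assumed value for a widely distributed small molecule and stands in for creatinine.

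**Step 3: which model is closer?** The Albutein label (Appendix 1, section 12.3) reports that in healthy subjects less than 10% of infused albumin leaves the circulation in the first 2 hours. That supports slow movement of large proteins over a session, but it is a figure for albumin, not for the enzymes or troponin. The protocol itself expects plasma proteins to fall with exchange: coagulation factors in 5.2.2.4 and immunoglobulins in 5.2.2.6.

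**Step 4: does the SAP offset it?** No. There is no dilution correction, baseline is unwashed, and these analytes have no pre-exchange value to use.

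**The case against.** The size is assumed. No passage gives a washout fraction or the plasma share of ALT, AST, LDH or troponin. That stands: the direction of the washout effect is secure, the 37% is not.

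Post-exchange sampling may be intended to catch injury caused by the procedure. That is a reason to keep the sample after the session. It does not explain the absence of one before, and without a pair, release and dilution cannot be separated.

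A reader might infer several stronger things that the documents do not support.
- *That injury is masked.* It is attenuated. Under the harshest central case 3 x ULN still reads above normal and 10 x ULN reads 3.68 x. Physical examination and adverse event review precede every exchange (6.2.2).
- *That kidney injury is hidden too.* Creatinine shares the timing, but on the assumed f of 0.1 it loses only about 10%.
- *That active arms must show fewer toxicity shifts than sham.* If exchange causes true release, that works against washout, so the net ordering is not fixed. All safety analyses are descriptive (SAP 9.1.5, 9.2.3), so no formal test turns on it.
- *That decisions on the next session are corrupted.* The postponement and suspension criteria in Protocol 5.2.1 use coagulation parameters and platelets, which are scheduled before and after. None uses these five analytes. Only general investigator judgement is exposed.
- *That every active patient is affected.* The 18 Version 1.0 patients had laboratory values only at baseline, the intermediate visit, LVPE4, LVPE7, LVPE10 and the final visit (SAP 2.1).

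Pre-exchange plasma is also stored at -70°C for possible future assays (6.2.2), so retesting may be possible, though it is not planned.

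**Conclusion.** The point holds in a limited form. At FPE1-FPE6, active-arm AST, ALT, LDH and troponin are read after washout and sham values are not, and the SAP sets both against an unwashed baseline. The washout bias is downward for any marker that stays largely in plasma. Its size is about a 2.7-fold reduction under the one-compartment assumption (2.2- to 3.3-fold for 0.8-1.2 plasma volumes), or 2-fold if half is removed. In practical terms, rises up to roughly 2-3 x ULN may read as normal or only slightly raised.

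Text and schedule agree on FPE1-FPE6, so this is a weakness of design and analysis, not a contradiction. The disagreement between Protocol 6.2.4 and Appendix 8 on the maintenance period is separate and needs reconciling. I have high confidence in the timing and the arm asymmetry, and medium confidence in the size.

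**What to change.** 1. **Protocol 6.2.2 and Appendix 8:** change A to B+A for the five analytes at FPE1-FPE6. Liver and kidney biochemistry shares the 10 mL draw with the proteinogram (6.2.6), which is already run before each session. Troponin is not listed for that tube and needs its own aliquot for the central laboratory. Keep the post-exchange sample: a pre-exchange draw a week later cannot replace it for an acute troponin rise.
2. **Protocol 6.2.3 and Appendix 8:** add the five analytes to the intermediate-visit blood draw, so that a value not preceded by a same-day exchange exists after FPE6.
3. **SAP 7.2.4:** base change from baseline, CTC AE shifts and arm summaries for these analytes on pre-exchange and intermediate-visit values. Report post-exchange values separately and label them as affected by washout.
4. **SAP section 7:** exempt these analytes from the last-non-missing rule, which would otherwise pick the post-exchange value again. State which value is baseline, because under the present definition a new FPE1 pre-exchange result would replace screening.
5. **Protocol 6.2.4 and Appendix 8:** reconcile the text with the blank LVPE cells for these analytes.

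The pre-exchange value removes same-session washout only; any carry-over from the previous week is not quantified here. If the sessions are already complete, items 3 and 4 reduce to labelling the comparisons as washout-affected, with retesting of stored pre-exchange plasma where feasible.

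Cost: six pre-exchange sets plus one at the intermediate visit, so about seven extra sets of routine assays per patient, and edits to the schedule and SAP. No new visit or venepuncture is needed.
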